3.0 PROTOCOL SUMMARY

Title	Combining Pregabalin (LYRICA®) with Lofexidine (LUCEMYRA™): Can it Increase the Success of Transition to Naltrexone?						
Short Title	Pregabalin and Lofexidine for opioid withdrawal						
Protocol Version	7.0						
Phase	Phase 2						
Methodology	Double-blind placebo-controlled parallel group clinical trial						
Study Duration	24 months						
Study Centers (3)	 University of Pennsylvania Center for Studies of Addiction in Philadelphia Pennsylvania Columbia University in New York City, New York Mountain Manor in Baltimore, Maryland 						
Objective (Primary)	To investigate whether pregabalin-Lyrica® (PGB) combined with Lofexidine-Lucemyra® (LFX) can reduce opioid withdrawal-related subjective effects						
Objective (Secondary)	To investigate, if the PGB/LFX combination can increase the proportion of patients with an opioid use disorder (OUD) who complete detoxification and transition to antagonist treatment with extended- release injectable naltrexone VIVITROL® (XR-NTX)						
Number of Subjects	90 subjects. 60 randomized to PGB/LFX; 30 to PGB-PLA/LFX						
Inclusion Criteria	 Male and/or female subjects ≥ 18 years of age Meet DSM-5 criteria for an Opioid Use Disorder with physiologic features. Have 2 or more of the 11 DSM 5 criteria for opioid disorder including tolerance and withdrawal features in the last 12 months Interested in opioid antagonist treatment Have used opioids in 20 of the past 30 days Have a stable address in the local area; not planning to move; have documents for ID check Absence of medical or psychiatric conditions that are likely to interfere with study participation Have a 12 lead ECG demonstrating a QTc ≤450 msec and a QRS interval ≤120 msec. The site PI has the final determination for inclusion into the study for ECGs unless there is a question of QT prolongation or other factors (QTc/Fri uses the Fridericia formula (QTc = QT/RR(1/3)). If consultation is needed, the PENN cardiologists and the medical monitor should be contacted. If female, have a negative pregnancy test, and uses adequate contraception if of childbearing potential 						

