9.1 GENERAL DESIGN

9.1.1 Phase 1: Outpatient Pre-Screening (Up to 30 days before hospital admission).

Study inclusion and exclusion criteria will be assessed to make sure the subject meets admission requirements. Those who meet requirements will be given information and details of the study including the timeline, potential risks and benefits, inpatient requirements, confidentiality, and told that participation is voluntary. They will be asked to read the informed consent and encouraged to ask questions, then given a quiz in which they must answer 9 of 10 answers correctly (three retries allowed). Potential subjects will then be asked to sign the informed consent and given a copy.

Once consented, subjects will be screened for up to 30 days to include the following: completion of a locator information form, concomitant medications used in the past 30 days, physical, medical history, complete blood cell count (CBC) with differential and PLT, INR, CMP with magnesium and calcium, urinalysis with reflex microscopy, urine drug screen, a fentanyl urine test, a xylazine urine test, a urine pregnancy test, ECG, creatine kinase test, an eGFR calculation, a Child-Pugh score (liver function), MINI assessment for Opioid Use Disorder with physiologic features (e.g. withdrawal), Insomnia Severity Index (ISI), Clinical Opioid Withdrawal Scale (COWS), Short Opioid Withdrawal Scale (SOWS-G), vital signs (can use manual blood pressure check if considered necessary), Timeline Follow- back (TLFB), Clinical Global Impression Scale (CGI), Hamilton Depression and Anxiety scales (HAM- D, HAM-A), Columbia-Suicide Severity Rating Scale (CSSR-S), an alcohol breathalyzer test, hepatitis B and C tests. Those meeting admission criteria will be asked to report to the inpatient unit on Monday through Friday; randomization will occur at hospital admission. Each collaborating program will enroll around 30 subjects, 20 to receive pregabalin plus lofexidine and 10 to receive placebo pregabalin plus lofexidine. The Pharmacy or designated physician or nurse at each site will receive pre-packaged blinded medications from PENN IDS. All study staff will be blinded.

9.1.2 Phase 2: Inpatient Detoxification (Days 1 thru 7).

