9.1.3 Phase 3: Inpatient XR-NTX Dosing (Day 8 or 9)

On day 8, subjects will be offered an injection of XR-NTX following naloxone challenge starting with a split dose an option of 0.2 mg first, wait 10-20 minutes, then 0.6 mg (0.8 mg I.M of naloxone total) An injection of Vivitrol is optional, only if the subject is interested in the XR-NTX treatment), and only if the COWS does not rise above 10 (COWS) within 15-30 minutes after the challenge. Subjects will be offered a second XR-NTX dose in the outpatient research clinic 4 to 5 weeks after the Day 8/9 injection if they wish to continue XR-NTX and have been unable to find a community provider. Subjects who fail the naloxone challenge on Day 8 will receive symptomatic treatment, observed until symptoms resolve, and be offered an opportunity for a repeat

challenge and injection on day 9. Note:

Note: XRNT may be given to patients after a Naloxone challenge in Pts about to go AMA from hospital if the naloxone challenge results suggest an absence of physiologic dependence.

The following assessments will be conducted before the XR-NTX injection:

- 1) CK test drawn before IM Injection of naloxone (PGB can elevate CK)
- 2) Vital Signs (blood pressure sitting)
- 3) Adverse Events Review
- 4) Urine Pregnancy Test
- 5) VAS scale
- 6) ISI
- 7) SOWS-G
- 8) POSS
- 9) UDS
- 10) Urine Fentanyl test
- 11) urine xylazine test
- 12) COWS
- 13) Naloxone Challenge*
- 14) Concomitant Medication Review
- 15) C-SSRS

ADMINISTRATION OF EXTENDED-RELEASE NALTREXONE

The following assessments will be conducted after the XR-NTX injection:

- 1) CGI
- 2) HAM-A, HAM-D
- 3) Inspection of injection site
- 4) Comfort medication(s) (PRN)

(It is permissible to give comfort medication at visit 8 for Day 8, 9, and at Day 10 for visit 10, 11, 12, 13, 14 and 15. No comfort medication will be given by the study after Day 15. Comfort medication needed after Day 15 will be considered non-study follow-up care. Patients can get comfort medications even if they don't opt for XR-NTX).

* Optional. Subject can opt not to receive this treatment. The Study Physician will discuss with the subject other available options. All assessments for Day 8 except the challenge and XR-NTX will still be collected.

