10.11 STUDY MEASURES; SEE TABLES 1 FOR SCHEDULES OF ADMINISTRATION

- 1. **Medical History:** Done by the appropriate clinical delegated individual at screening
- 2. Physical/Weight: Done at Screen; and at Day 15
- 3. Pulse and blood pressure: done sitting and standing 1X at screen, done Day 1 through Day 7 done before receiving Study Medication and 1 2 hours after receiving medication, 1X on Day 8, 1X (sitting only) on Day 10 (sitting only), and 1X on Day 15
- 4. ECG: 1X at Screen, 1X each day for Day 1 through Day 7
- 5. Complete Blood Count with diff and PLT: Done at Screening and Day 10
- **6.** Chemistry and calcium: Done at Screening and at Day 10 or Day 15 if not obtained at Day 10
- 7. Magnesium Screening (magnesium need not be repeated at EOS)
- 8. Creatine Kinase at screening and Day 8, and early termination
- 9. Hepatitis B and C done at screening
- 10. Urinalysis with reflex microscopy: Done at Screening and Day 10
- **11. Urine Toxicology Drug Screen.** CLIA Waived and FDA approved on-site test with Buprenorphine, or get an additional buprenorphine test, done at screen, day 8/9, day 10, and day 15.
- **12. Urine Fentanyl**. Done at Screen, Day 1, Day 8/9, Day 10, and Day 15.
- 13. Urine Xylazine . Done at Screen, Day 1, Day 8/9, Day 10, and Day 15.
- 14. Urine pregnancy test: Screen and Day 1, Day 8/9 prior to the XR-NTX injection, and at Day 15
- 15. Adverse Events: Collected by research staff at each visit, Day 1 through Day 15
- **16. Clinical Global Impression Scale (CGI;** Guy,1976): A brief severity rating of overall health at time of interview using a 7-point Likert scale. Completed by a study staff person and the subject. Administered at day 1, day 8, and EOS
- 17. Clinical Opioid Withdrawal Scale (COWS; Wesson & Ling, 2003): An 11-item, staff administered instrument that measures objective signs of opiate withdrawal. Done 1X at screen, 2X daily Day 1 through Day 7, 2X (naloxone challenge) on Day 8* (optional), and 1X on Day 10, and 1X Day 15
- **18. Short Opioid Withdrawal Scale** (SOWS-Gossop; Gossop, 1990): A 10-item, staff administered scale that measures patient's perceptions of opiate withdrawal. Done 1X at screen; 2X daily Days 1 Day 7; and 1X on Days 8,10, and 15.
- **19. CONCOMITANT Medication** (CONMEDS): Any prescribed or non-illicit non-Study Medications used 30 days before screening, and on Day 1 through EOS

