13.0 STATISTICAL PLAN

13.1 DATA ANALYSES

[name], the CSA Statistician, and his staff will perform data analyses. Prior to analyses, standard data screening/cleaning procedures will be applied. These procedures will screen the data for data-entry errors, check for outliers, assess the extent and pattern of missing data, and check that appropriate assumptions of normality are met whenever necessary.

13.2 **SAMPLE SIZE DETERMINATION**

Power Analyses: The primary goal of this study is to determine if the PBG/LFX combination versus LFX/PGB-PLA is safe and effective in OUD individuals, and shows a reduction in opioid–related withdrawal effects greater than lofexidine alone. To assist in this determination, we provide power for the primary comparison of longitudinal subjective withdrawal measures, comparing the groups on rate of decrease across days, using a linear group by time effect for the mixed effects models described above. We have one primary outcome, so use an alpha level of 0.05, and we use two- sided tests. 90 subjects, approximately 30 from each of three sites (MMTC and PENN might have more than 30), who will be randomized into two groups, with 30 assigned to LFX/PGB-PLA, and 60 to LFX plus a starting daily dose of 400 mg of PGB and increasing to 600mg PGB on day 2. Assuming an overall dropout rate of 40%, and within-subjects' correlations of 0.5, the methods of Hedeker et al (Hedeker, Gibbons and Waternaux, 1999) show that this provides 80% power for a group by linear time interaction effect of Cohen's d=0.44 standard deviations between the two groups.

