13.4 SAFETY OUTCOMES

- 13.4.1 Suicidality. We will compare the groups on presence of active suicidal ideation on the basis of the C-SSRS, which will be administered daily. We define Active Suicidal Ideation to be an endorsement of either Question 4 (active ideation without plan) or 5 (active ideation with plan). If there is sufficient variability in these repeated binary outcomes, we will compare the groups using a mixed effects logistic regression model, similar to the linear mixed effects models described above for the primary outcome; if variability is too low, we will use a (non-mixed-effects) logistic regression model to compare the groups on proportion of participants reporting active ideation at any time in the period
- **13.4.2 Sedation.** The POSS will be administered four times a day on dose days, yielding a set of repeated measures on the POSS score for each participant. We will compare the groups on this score, using linear mixed effects models similar to those described above for the primary outcome.
- **13.4.3** Elevated Creatine Kinase. On day 8 of detoxification, participants will be classified as having elevated creatine kinase if their level is more than three times their screening level. We will compare groups on this response using a logistic regression model with site and group as explanatory variables.
- **13.4.4_Edema**. We will compare groups on the proportion of participants whose study medications were discontinued due to peripheral edema, using a logistic regression model with site and group as the explanatory variables.

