19.2 MEDICATION DISCONTINUATION CRITERIA

All randomized subjects are included in the intent-to-treat analysis. All subjects who prematurely discontinue treatment will be scheduled for a final evaluation and end-of trial visit (unless these two fall within 2 weeks of each other), and the follow up visit. Subjects are not dropped from all study activity unless they request to not be contacted or cannot be located for assessment.

Subjects will be informed at the consent session that medications may be held or discontinued due to intolerable side effects, hypotension or other problematic cardiovascular effects, or extreme lab values confirmed by a repeat test. (AST or ALT levels greater than 4 times upper limit of normal; elevated BUN, creatine kinase, or other evidence of renal damage). Subjects will also be informed at the consent session that he or she may be discontinued from study treatment due to: 1) Development or exacerbation of significant psychiatric or medical symptoms which necessitate admission to a medical unit or an intervention different from that provided by the protocol; 2) Clinical deterioration for any reason or a clinical status which necessitates inpatient admission; 3) Prolonged QTc after repeat ECG; 4) Blood pressure is less than 90 mm Hg (systolic) or less than 60 mm Hg (diastolic). For sitting to standing blood pressure (orthostatic change), if there is a change in systolic blood pressure of more than 20mm or diastolic blood pressure more than 10mm HG, the dosing nurse or physician may hold the lofexidine or pregabalin dose until the next dose and then recheck (can use manual blood pressure check if considered necessary). If at any point blood pressure is less than 90/60 the nurse or physician should also hold the lofexidine or pregabalin dose and consult a study physician. If for any dose, the blood pressure results remain below the previously stated minimum mmHg by the next scheduled dose, the next dose may be reduced or withheld. Dosing discontinuations can be discussed with the Lead PI and the medical monitor if it impacts subject continuation in the dosing part of the study. The reason the subjects misses their next dose of Study Medication or discontinues from Study Medication must be documented in the subject's casebook

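### The only CK comparison is a yes/no against each patient's own screening value: it can mislabel values as elevated or not, and it has low power for rises up to about 2-fold

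*Combined protocol and SAP*

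**What the plan says.** Section 13.4.3 takes the Day 8 value and states that "participants will be classified as having elevated creatine kinase if their level is more than three times their screening level". It continues: "We will compare groups on this response using a logistic regression model with site and group as explanatory variables". It specifies no continuous CK analysis, no count against the ULN, no expected rate and no handling of an arm with zero events.

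The protocol gives its reason for measuring CK in Section 9.1.3: "CK test drawn before IM Injection of naloxone (PGB can elevate CK". Section 10.11 sets the timing: "Creatine Kinase at screening and Day 8, and early termination". The screening value may be some weeks old at admission, because Section 9.1.1 says "Once consented, subjects will be screened for up to 30 days to include the following". The entry criteria (Sections 10.1 and 10.2) contain no CK limit. Section 19.2 names CK among the laboratory findings that can lead to holding or stopping medication, "elevated BUN, creatine kinase, or other evidence of renal damage", without a level for CK.

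**The concern.** CK is a named safety outcome for a combination that Section 10.13.3 says has not been tested, in a trial meant to inform a larger one (Section 7.1.6). The between-group CK result should therefore be readable.

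Two features work against that. First, the word elevated is attached to a measure of change, so the count can include values inside the normal range and omit high values in patients who started high. Second, a continuous measurement with its own baseline is cut at one high threshold. Few patients cross it unless the shift is large, so a null result would say little about a moderate rise.

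**Working it through.** The plan states no CK rate, sample size or power, so there is no figure of its own to reproduce.

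**Definition (no assumptions needed).** Let screening CK be k × ULN. Day 8 CK is flagged only if it exceeds 3k × ULN.
- k = 0.3: threshold 3 × 0.3 = 0.9 × ULN, so 0.91 × ULN is flagged although normal. The same can happen for any k below 1/3.
- k = 2: threshold 3 × 2 = 6 × ULN, so 5.9 × ULN is not flagged.

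**Numbers available.** Section 3.0 gives "60 randomized to PGB/LFX; 30 to PGB-PLA/LFX". Section 13.2 has "Assuming an overall dropout rate of 40" per cent. If loss is equal in both arms and leaves no Day 8 value, 60 × 0.6 = 36 and 30 × 0.6 = 18 remain.

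**Assumptions (not in the documents).** CK is log-normal with log-SD s = 0.5 to 0.8 at each time. The correlation between log screening and log Day 8 CK is ρ = 0.5. Pregabalin multiplies Day 8 CK by g. Tests are two-sided at 0.05, the level Section 13.2 states for the primary outcome. Fisher's exact test on the two arms stands in for the logistic regression, with site left out.

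**Formulas.**
- The SD of the log ratio of Day 8 to screening is s√(2(1 − ρ)) = s. The flag rate is 1 − Φ((ln 3 − ln g)/s), with g = 1 for placebo.
- For log CK adjusted for screening, the residual SD is s√(1 − ρ²) = 0.866s. The standard error of the group difference is 0.866s × √(1/36 + 1/18) = 0.25s. Power is about Φ(ln g/(0.25s) − 1.96).
- Example, g = 1.5 and s = 0.5: placebo flag rate 1 − Φ(1.099/0.5) = 1.4%; pregabalin 1 − Φ(0.693/0.5) = 8.3%. Log CK: 0.405/0.125 − 1.96 = 1.28, about 90% (89% with the t distribution).

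| True rise g | s | Flag rate, placebo / PGB | Power, >3× rule | Power, adjusted log CK |
|---|---|---|---|---|
| 1.5 | 0.5 | 1.4% / 8.3% | 1% | 89% |
| 1.5 | 0.8 | 8.5% / 19.3% | 11% | 51% |
| 2 | 0.5 | 1.4% / 20.9% | 40% | >99% |
| 2 | 0.8 | 8.5% / 30.6% | 40% | 92% |
| 3 | 0.5 | 1.4% / 50% | 99% | >99% |
| 3 | 0.8 | 8.5% / 50% | 89% | >99% |

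**Sensitivity.**
- With no dropout (60 against 30), power for a 1.5-fold rise is 8–19% against 72–99%.
- With ρ = 0.8, it is under 1% against 81–100%.
- A separate calculation on the log ratio itself, with SD 0.7 and a doubling of CK, gives 47% against 93%.
- The test matters, and Section 13.4.3 does not name one. For rates of 2% against 20% at 18 and 36 patients, power is 1% with a Wald test, 41% by normal approximation and 65% with a likelihood-ratio test. All are below log CK.

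**Sparse data.** The chance of no flagged placebo patient among 18 is (1 − 0.014)^18 = 78% at s = 0.5 and (1 − 0.085)^18 = 20% at s = 0.8. If any pregabalin patient is then flagged, the fitted odds ratio is infinite.

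**The case against.** The strongest reply has five parts.

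1. A reader might infer that a real CK rise on pregabalin would usually go undetected. The documents do not support that. They give no CK variance, event rate or expected effect, and a 3-fold shift is found by the plan's own rule in about 89–99% of trials under the same assumptions. CK is also watched outside 13.4.3. Section 10.12 requires review of laboratory reports and repeat of significantly abnormal values, Section 15.4 makes confirmed abnormalities adverse events, Section 19.2 lists CK, and Section 19.1 gives the monitoring board unblinded adverse event review. This stands: a marked rise need not be missed by the trial. What those routes do not give is a between-group estimate.

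2. A reader might also infer that testing CK above 3 × ULN would cure the problem. It would not. With an assumed median of 0.5 × ULN, that test has 0–1% power for a 2-fold rise, and for true shifts from none to 2-fold at least one arm is empty in 79–100% of trials. ULN counts describe; they do not add power. With that median, a 2-fold shift only brings the median to the ULN, so the shifts for which power is low are moderate ones.

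3. The ULN limits for ALT and AST are entry and discontinuation rules, not group comparisons, so they do not show an inconsistency. Change from baseline is a legitimate measure, and Section 13.8 uses it for vital signs.

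4. An infinite odds ratio does not end the analysis, since likelihood-ratio or exact inference remains possible. The fair remark is that the plan does not say which would be used.

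5. Section 13.2 claims power only for the withdrawal score, and Section 7.1.6 calls the safety data preliminary. Low power here is a limitation, not a contradiction.

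None of this explains why a change measure is called elevated, or why a continuous value with a baseline is analysed only as a yes/no.

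**Conclusion.** The point holds in limited form. The labelling fault follows from the rule and the absence of a CK entry limit, whatever the ULN, but it concerns this outcome only. The loss of power is conditional: for rises up to about 2-fold, the >3× rule has about 1–11% (1.5-fold) and about 40% (2-fold), where adjusted log CK has about 50–90% and 92–100%. Those figures rest on 36 against 18 patients, log-normal CK with log-SD 0.5 to 0.8, correlation 0.5 and Fisher's test. A likelihood-ratio test would narrow the gap without closing it. Nothing here shows that large CK rises would escape the trial, or that the plan contradicts itself. It is an inefficient and poorly named analysis that should be improved.

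**What to change.** In Section 13.4.3:
- Make the between-group comparison a linear regression of log Day 8 CK on group, site and log screening CK. Report it as a ratio of geometric means with a 95% confidence interval.
- Keep the >3× count as a descriptive measure, relabelled 'more than 3-fold increase from screening'.
- Report counts against the laboratory ULN, and a shift table from screening, by arm. Present both descriptively, not as a powered test.
- Say how CK values taken at early termination are used. They are collected, but 13.4.3 names only Day 8, while Section 13.6 analyses all randomised subjects.

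The cost is SAP wording. Screening and Day 8 CK are already collected. Section 10.12 has each site use its own laboratory, so the ULN must be taken from each site's report if it is not already recorded. The small downside is that the headline becomes a ratio of means instead of a responder rate.

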- If the repeated readings are not within this range as defined by the protocol, hydrate the patient and study medication should be administered at the next scheduled dosing time provided they are in an acceptable range, as defined by the protocol. Retest the BP within an hour. Depending on the results of the BP retest, the physician has the discretion to give full dose, reduced dose, or hold the dose of study medication until the next scheduled dosing time.

Dosing should be given per the protocol scheduled times of 8:00, 12:00, 16:00, and 20:00. However, when dosing cannot be given at the protocol scheduled times, Study Medication can be given up to 1 hour pre or post the scheduled dose time. On day 1, if dosing cannot be given at the 12:00 scheduled time, after 2 hours, wait until the next scheduled 16:00 dose. In case of scheduled dosing changes, medication cannot be scheduled less than a minimum of 3 hours apart.

- **7.3.4** Potential Risks: These include AEs to PGB, LFX, and XR-NTX (for those who transition to it); potential adverse interactions between PGB and LFX; and a small risk from venipuncture. Clinical trials are conducted under widely varying conditions thus adverse reaction rates in clinical trials cannot be directly compared to rates in clinical trials of another similarly-acting drug, and may not reflect the rates observed in clinical practice.
- **7.3.5_PGB associated AE's:** In controlled and uncontrolled trials across various patient populations during premarketing development more than 10,000 patients received PGB; approximately 5000 for 6 months or more; over 3100 for 1 year or more; and over 1400 for at least 2 years.
- **7. 3. 6** Most common AE's leading to discontinuation of PGB. In premarketing trials of all populations combined, 14% of patients treated with PGB and 7% of patients treated with placebo discontinued treatment prematurely due to AEs. AEs most frequently leading to discontinuation were dizziness (4%) and somnolence (3%). In the placebo group, 1% of patients withdrew due to dizziness and <1% withdrew due to somnolence. Other adverse reactions that led to discontinuation more frequently in the PGB group compared to placebo were ataxia, confusion, asthenia, thinking abnormal, blurred vision, incoordination, and peripheral edema (1% each).

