- **7.3.7** Most common AE's in all pre-marketing controlled PGB studies. In premarketing controlled trials of all populations, dizziness, somnolence, dry mouth, edema, blurred vision, weight gain, and "thinking abnormal" (mostly difficulty with concentration/attention) were more commonly reported by subjects treated with PGB than placebo (≥5%, twice the placebo rate).
- **7.3.8_AE's Leading to Discontinuation in controlled PGB trials.** For those of neuropathic pain in patients with diabetic neuropathy: 9% of patients treated with PGB and 4% of patients treated with placebo discontinued prematurely due to AEs. In the PGB group, the most common reasons for discontinuation were dizziness (3%) and somnolence (2%). In comparison, <1% of placebo patients withdrew due to dizziness and somnolence. Other reasons for discontinuation with greater frequency in the PGB than placebo groups were asthenia, confusion, and peripheral edema. Each led to withdrawal in approximately 1% of patients. Table 4 lists AEs, regardless of causality, occurring in ≥1% of patients with neuropathic pain associated with diabetic neuropathy in the PGB group for which the incidence was greater than placebo. A majority of PGB patients had AEs with a maximum intensity of "mild" or "moderate".

Table 4: AE'S in trials of Neuropathic Pain Associated with

Diabetic Neuropathy in at least 1% of pregabalin-treated patients

Body system - Preferred term	75 mg/day [N=77]	150 mg/day [N=212] %	300 mg/day [N=321] %	600 mg/day [N=369] %	All PGB* [N=979] %	Placebo [N=459]
Body as a Whole						
Asthenia	4	2	4	7	5	2
Accidental injury	5	2	2	6	4	3
Back pain	0	2	1	2	2	0
Chest pain	4	1	1	2	2	1
Face edema	0	1	1	2	1	0
Digestive System						
Dry mouth	3	2	5	7	5	1
Constipation	0	2	4	6	4	2
Flatulence	3	0	2	3	2	1
Metabolic and Nutr	ritional					
Peripheral edema	4	6	9	12	9	2
Weight gain	0	4	4	6	4	0
Edema	0	2	4	2	2	0
Hypoglycemia	1	3	2	1	2	1
Nervous System						
Dizziness	8	9	23	29	21	5
Somnolence	4	6	13	16	12	3
Neuropathy	9	2	2	5	4	3
Ataxia	6	1	2	4	3	1
Vertigo	1	2	2	4	3	1
Confusion	0	1	2	3	2	1
Euphoria	0	0	3	2	2	0
Incoordination	1	0	2	2	2	0
Thinking abnormal [†]	1	0	1	3	2	0
Tremor	1	1	1	2	1	0
Abnormal gait	1	0	1	3	1	0
Amnesia	3	1	0	2	1	0
Nervousness	0	1	1	1	1	0
Respiratory System						
Dyspnea	3	0	2	2	2	1
Special Senses						
Blurry vision [‡]	3	1	3	6	4	2
Abnormal vision	1	0	1	1	1	0

^{*} PGB: pregabalin

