13.6 SUBJECT POPULATION FOR ANALYSIS

All subjects who are randomized will be analyzed according to the Intent-to-Treat study design.

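### Section 13.4.4 measures edema only by drug discontinuation, at about 1% in the protocol's own data, and analyses it with a logistic model that would seldom give a finite group estimate

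*Combined protocol and SAP*

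**What the plan says.** Edema is one of four safety outcomes in Section 13.4. Section 13.4.4 consists of one sentence, which opens with the definition: "We will compare groups on the proportion of participants whose study medications were discontinued due to peripheral edema". The rest of that sentence names the method, an ordinary logistic regression in which site and group are the only predictors. Nothing is said about what happens if events are few or absent. Section 13.4.1, on suicidality, does name a simpler model for the case of too little variability.

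The group sizes are "60 randomized to PGB/LFX; 30 to PGB-PLA/LFX" (Section 3.0), and Section 13.6 adds: "All subjects who are randomized will be analyzed according to the Intent-to-Treat study design".

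The protocol gives two background rates for this event on pregabalin:

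- Section 7.3.6, all premarketing populations: "incoordination, and peripheral edema (1% each". The list is introduced as "Other adverse reactions that led to discontinuation more frequently in the PGB group compared to placebo", so the placebo rate is lower, but it is not stated.
- Section 7.3.8, diabetic neuropathy trials, on reasons for discontinuation that include peripheral edema: "Each led to withdrawal in approximately 1% of patients".

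Table 4 in Section 7.3.8 gives peripheral edema of any kind as 6% at 150 mg/day, 9% at 300 mg/day, 12% at 600 mg/day and 2% on placebo. Section 9.1.2 allows pregabalin to be withheld or reduced for peripheral edema.

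**The concern.** The definition picks the rarest form of the event, and the model needs events in both arms. If either arm has none, the maximum-likelihood odds ratio for group is zero, infinite or undefined, and the planned comparison gives no usable estimate.

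The definition also loses cases. A patient whose edema is managed by a held or reduced dose, and who then continues, is counted the same as a patient without edema. The outcome could show no events in either arm while edema is in fact more common on pregabalin.

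Section 7.1.6 presents the trial as a precursor to a larger one, and Section 7.1 says it is to supply preliminary safety and tolerability data on the combination. A table with zero discontinuations could then be taken for reassurance that it does not give.

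**Working it through.** The plan states no power, expected count or sample size for edema, so there is no figure to reproduce.

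**Inputs.** 60 and 30 patients (Sections 3.0 and 13.6); 1% discontinuation for edema on pregabalin (Sections 7.3.6 and 7.3.8). The placebo rate is an assumption, 0% to 1%, capped at the pregabalin rate because Section 7.3.6 says these events were more frequent on pregabalin.

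**Events as defined.** Expected on pregabalin: 60 × 0.01 = 0.6. Chance of none: 0.99^60 = 0.547.

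**Chance of a finite group odds ratio.** At least one event is needed in each arm:

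P(finite) = [1 − (1 − p1)^60] × [1 − (1 − p0)^30]

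At p1 = 1% and p0 = 0.5%: (1 − 0.547) × (1 − 0.860) = 0.063. Other values:

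| Pregabalin rate | Placebo 0% | 0.1% | 0.25% | 0.5% | 1% |
|---|---|---|---|---|---|
| 0.5% | 0% | 0.8% | 1.9% | 3.6% | 6.8% |
| 1% | 0% | 1.3% | 3.3% | 6.3% | 11.8% |
| 2% | 0% | 2.1% | 5.1% | 9.8% | 18.3% |
| 3% | 0% | 2.5% | 6.1% | 11.7% | 21.8% |

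At 1% on pregabalin, neither arm has an event in 40% (placebo 1%) to 55% (placebo 0%) of trials. A simulation with 20 + 10 patients at each of three sites agreed with the 1% row where it was run. It also showed all coefficients, site included, to be finite in at most 1.3% of trials at 1% on pregabalin. With 0/30 on placebo, 8/60 discontinuations on pregabalin would be needed for Fisher p < 0.05 (p = 0.048; 7/60 gives 0.090).

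**Any peripheral edema instead, at Table 4 rates (12% vs 2%).**

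- Expected events: 60 × 0.12 = 7.2 and 30 × 0.02 = 0.6.
- Chance of none on pregabalin: 0.88^60 = 0.0005.
- Chance of none on placebo: 0.98^30 = 0.545.
- Finite ordinary odds ratio: (1 − 0.0005) × (1 − 0.545) = 0.454.
- Fisher power by enumeration: 24%.

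**At half those rates (6% vs 1%).**

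- Expected events: 3.6 and 0.3.
- Chance of none on pregabalin: 0.94^60 = 0.024.
- Finite ordinary odds ratio: (1 − 0.024) × (1 − 0.740) = 0.254.
- Fisher power: 2%.

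**What estimation would give.** For 7/60 (11.7%), the 95% interval is 5.8% to 22.2% (Wilson) or 4.8% to 22.6% (exact).

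**The case against.** **The threshold is a legitimate choice.** Discontinuation is a clinically consequential event, and Section 10.12 lists adverse events leading to discontinuation among the safety measures. This stands, and is a reason to keep the count. It does not make a regression on 0.6 expected events informative.

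**The data are not lost.** All edema adverse events can still be recorded under Sections 13.7 and 15.6, and the arm proportions for discontinuation can be reported whatever the model does. This also stands: what fails is the planned model estimate, not all reporting. But no other between-group comparison of edema is specified.

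**The method could be changed without the definition.** True: an exact or penalised method copes with empty arms. It would still rest on almost no events, and would still miss edema managed by a held or reduced dose.

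**Table 4 is a poor guide to this trial.** The 12% belongs to 600 mg/day in diabetic neuropathy. Here 600 mg is scheduled on Days 2 to 4 only, falling to 100 mg on Day 7 (Table 3), so 12% is probably high. This is why half the rates are also shown.

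**Ascertainment.** Section 15.6 relies on questioning, with examination as appropriate, and Table 1 schedules no edema examination during dosing. Mild edema may be picked up unevenly across sites. This stands as a limit of the fix.

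A reader might also infer three stronger claims that the documents do not support:

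- That the planned model is certain to fail, or fails in some single percentage of trials. The placebo rate is not given, so only a range can be stated.
- That widening the definition cures the problem by itself. At the Table 4 rates an ordinary odds ratio is still not finite in more than half of trials.
- That edema is a stated objective. Sections 8.1 and 8.2 do not mention it; it is a named safety outcome.

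**Conclusion.** The point holds as a sparse-data and definition problem in one safety outcome. At the protocol's own rate of about 1%, between 88% and 100% of trials would give no finite group odds ratio, for a placebo rate of 0% to 1%. Even at 3% against 1% the figure is about 78%.

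This rests on the assumed placebo range, and on a 1% rate taken from other populations, often with longer exposure: Section 7.3.5 has about 5,000 of more than 10,000 premarketing patients treated for six months or more. The true rate over seven days with lofexidine is unknown, but the conclusion survives pregabalin rates from 0.5% to 3%.

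The primary and secondary analyses are untouched. It is a minor recommendation.

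**What to change.** Amend Section 13.4.4 in three respects:

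1. **Outcome:** the proportion of patients with any treatment-emergent peripheral edema adverse event from first dose to Day 15, which is within the existing collection period (Section 10.11).
2. **Method:** counts by arm and the risk difference with an exact interval, or a Firth-penalised logistic model on group.
3. **Discontinuations for edema:** retained as a descriptive count by arm.

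Items 1 and 2 belong together, because neither alone deals with both the lost cases and the empty arms.

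The cost is a short change of wording in Section 13. The adverse event record already holds coded terms and the action taken on study drug (Section 13.7), so no new form or visit is required. The price is that mild edema counts equally with severe, and that completeness depends on routine questioning at each site. The report should say so and present the result as an estimate, not as a test.
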